3.0 ELIGIBILITY

3.1 Inclusion Criteria

3.1.1 Age ≥ 18 years old, except sub-study 1

3.1.2 Competent and capable to sign informed consent

3.1.3 Subjects meeting the following criteria by arm:

3.1.3 Sub-Study 1:

- Age ≥40 years since the risk of prolonged disease that progresses to severe COVID-19 disease increases with age.
- PCR-positive for the SARS-CoV2 virus
- Fever or cough or shortness of breath
- ≤4 days since the first symptoms of COVID-19 and date of testing
- Not requiring hospitalization and is sent home for quarantine.
- Not taking azithromycin at the time of enrollment
- Symptomatic at the time of enrollment
- Must live within 30 miles of HUP or Penn Presbyterian Medical Center to facilitate drop-off of medication
- Must have access to a working computer, or smartphone and have internet access
- Must be willing to fill out a daily symptom diary
- Must be available for a daily phone call,
- Must take their own temperature twice a day
- Must be willing to report the observed symptoms and development of COVID-19 in the co-inhabitants of the residence at which the quarantine will be served.

Sub-Study 3 Health Care Worker Prevention

- Healthcare worker at HUP or PPMC (Healthcare worker is defined as: a UPHS employee that physically interact with COVID-19 patients e.g., doctors, nurses, respiratory techs, certified nursing assistants, emergency room techs, OB ultrasound techs).
- ≥20 hours per week of clinical work scheduled in the coming 2 months during the COVID-19 pandemic
- No fever, cough, or shortness of breath in the past 2 weeks unless a SARS-CoV-2 test was performed for these symptoms and the result was negative prior to enrollment

The PATCH Trial

- 3.1.4 Sub-studies 1 and 3: Willing to report compliance with HCQ in the form of a diary
- 3.1.5 Sub-Studies 1 and 3: Participants are willing to collect oral fluid using a simple applicator that is provided, and freeze these samples.
- 3.1.6 Not pregnant and/or breastfeeding, as determined below:
Sub-Study 1 and 3: Not known to be pregnant or breast feeding as determined through self-report

[All participants] 3.1.7 Patients must be able to swallow and retain oral medication and must not have any clinically significant gastrointestinal abnormalities that may alter absorption such as, but not limited to malabsorption syndrome, major resection of the stomach or bowels, gastric bypass, lap banding.

3.2 Exclusion Criteria

- 3.2.1 <18 years of age [Sub-Study 3]; <40 years old [Sub-Study 1]
- 3.2.2 Prisoner or other detained person
- 3.2.3 Allergy to hydroxychloroquine, 4 aminoquinolines, or quinine
- 3.2.2 Patients with known history of G6PD deficiency
- 3.2.2 Pregnant and/or breastfeeding, see above
- 3.2.3 Receiving any treatment drug for 2019-ncov within 14 days prior to screening evaluation (off label, compassionate use or trial related).
- 3.2.4 Co-enrollment onto another interventional COVID-19 study is not allowed.
- 3.2.5 Known history of retinal disease, including but not limited to, macular degeneration, retinal vein occlusion, visual field defect, diabetic retinopathy
- 3.2.6 Known history of interstitial lung disease, severe emphysema or asthma, or chronic pneumonitis unrelated COVID-19.
- 3.2.7 Taking any of the following medications that prolong Qtc: Chlorpromazine, Haloperidol, Droperidol, Quetiapine, Olanzapine, Amisulpride, Thioridazine
- 3.2.8 Due to risk of disease exacerbation patients with known porphyria or psoriasis are ineligible unless the disease is well controlled and they are under the care of a specialist for the disorder who agrees to monitor the patient for exacerbations.
- 3.2.6 Patients with serious intercurrent illness that requires active infusional therapy, intense monitoring, or frequent dose adjustments for medication including but not limited to infectious disease, cancer, autoimmune disease, cardiovascular disease.
- 3.2.7 Patients who have undergone major abdominal, thoracic, spine or CNS surgery in the last 2 months, or plan to undergo surgery during study participation.
- 3.2.8 Patients receiving cytochrome P450 enzyme-inducing anticonvulsant drugs (i.e. phenytoin, carbamazepine, Phenobarbital, primidone or oxcarbazepine) within 4 weeks of the start of the study treatment
- 3.2.9 History or evidence of increased cardiovascular risk including any of the following:
- Left ventricular ejection fraction (LVEF) < institutional lower limit of normal. Baseline echocardiogram is not required.
 - Current clinically significant uncontrolled arrhythmias. Exception: Participants with controlled atrial fibrillation
 - History of acute coronary syndromes (including myocardial infarction and unstable angina), coronary angioplasty, or stenting within 6 months prior to enrollment
 - Current \geq Class II congestive heart failure as defined by New York Heart Association

4.0 PARTICIPANT RECRUITMENT, CONSENT, AND REGISTRATION

4.1 Sub-study –specific flow of recruitment, consent, registration, drug supply

4.1.1 Sub-Study 1 Outpatient Recruitment, Consent and Registration Procedure:

1. Patients with a positive SARS-CoV-2 test are identified by a clinical lab.
For this sub-study, patients ≥ 40 with Fever or cough, or shortness of breath AND symptoms started 4 days or less before the patient came for testing
2. Delegated study team member will be notified of positive patients (as example: clinical research coordinators (CRC)).
3. Study team member screens the EPIC chart for specific eligibility criteria and calls the patient (if appropriate)
 - a. Informs the patient of positive SARS-CoV-2 result
 - b. Introduces the study and determines if the patient is interested in hearing more details from a clinician investigator
 - c. If interested, study team member sends consent via email/DocuSign to interested patient
4. Clinical Investigator contacts the interested patient
 - a. Conducts e-consent process with the patient and documents via telemedicine/DocuSign
 - b. If the DocuSign process fails due to technical difficulties, and the participant can print out the pdf, sign the consent form, take a digital photo and send the study, the consenting process can proceed. The clinical investigator must sign, date and time the printed signature page with the patient signature, and document the consenting process in EPIC.
 - c. Screens the participant for signs and symptoms that would warrant hospitalization (dizziness, shortness of breath at rest, orthostasis, low urine output).
 - d. Completes the eligibility checklist and signs it.
5. CRC links EPIC chart to study and emails IDS for randomization
6. IDS randomizes the participant Clinical Investigator uses PennChart to order the study drug IDS prepares blinded medication in bottles
7. Blinded study drug (HCQ or placebo) are dispensed to delegated study member and delivered to the participant's house or shipped. Study team includes oral fluid collection kits, nares swabs, mobile cardiac telemetry monitoring device (ZioAT, iRhythm Technologies). The patient must call the CRC to inform receipt of study drug. CRC documents this receipt. If for some reason this is not possible, drug will be shipped to the participant using an approved pharmacy shipping vendor.
8. Appropriately delegated and credentialed study team member calls the participant and reviews use of the study drug, establishes best contact information for response monitoring (See Section 8.5), and asks the patient to connect/wear the cardiac telemetry monitoring device. If the baseline, adjusted (Pre-treatment) Qtc is >500 , the patient will be removed from the study and advised to go to the emergency room for admission to the hospital for evaluation for inpatient monitoring. Since the half life of HCQ is many days, the activation of the ZioAT and transmission of the baseline QTc does not need to occur before starting study medication.

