Mobile Cardiac Telemetry: Participants will be provided with a mobile cardiac telemetry device (ZioAT, iRhythm Technologies). This technology will wirelessly transmit continuous monitoring to Irhythm, Inc. Irhythm will notify the study team for prolonged QTc, or life threatening arrhythmias in near real time. Dose adjustments will be performed as described below to achieve adjusted QTc <500 ms when necessary. Refusal to wear the mobile cardiac telemetry device will not prevent study participation and/or will not result in removal from the trial. Baseline QTc will be assessed by the cardiology Subl. Subsequent cardiac assessments will only be triggered by Irhythm alerts.

Oral fluid collection: Participants will be asked to collect oral fluid using the RNAPro-Sal collection kit manufactured by Oasis Diagnostics (<https://4saliva.com/products/rnapro-sal/>). These kits will be provided to the participant with the drug supply. The participant will have clear instructions on how to collect oral fluid on themselves. This process consists of inserting the gauze tip in the mouth for 4 minutes, removing and pushing the syringe to squeeze the fluid into the container. A video will be sent to the participant's email address and texted to them providing visual instructions on use. Participants should produce an early morning saliva sample from the posterior oropharynx (ie, coughed up by clearing the throat) before toothbrushing and breakfast, because nasopharyngeal secretions move posteriorly and bronchopulmonary secretions move by ciliary activity to the posterior oropharyngeal area while the patients are in a supine position during sleep. Participants will be instructed to collect oral fluid at the following time-points in the containers provided (before taking the first dose of study drug, day 3, day 7). The collected oral fluid should be placed in the freezer in a sealed container. This container will be collected after the participant is released from quarantine. The participant will then wipe the container surface with disinfectant and the ED van will come to pick up the sample. The van driver will open a bag and the participant will carefully place the container in the bag, so that the outside of the bag is not contaminated. If the participant becomes hospitalized with COVID-19, a primary contact for the participant will be contacted and if asymptomatic and/or COVID-19 negative the driver will pick up the saliva using the same procedure.

Nares swabs:

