Oral fluid collection: Participants will be asked to collect oral fluid using the RNAPro-Sal collection kit manufactured by Oasis Diagnostics (<https://4saliva.com/products/rnapro-sal/>). These kits will be provided to the participant with the drug supply. The participant will have clear instructions on how to collect oral fluid on themselves. This process consists of inserting the gauze tip in the mouth for 4 minutes, removing and pushing the syringe to squeeze the fluid into the container. A video will be sent to the participant's email address and texted to them providing visual instructions on use. Participants should produce an early morning saliva sample from the posterior oropharynx (ie, coughed up by clearing the throat) before tooth brushing and breakfast, because nasopharyngeal secretions move posteriorly and bronchopulmonary secretions move by ciliary activity to the posterior oropharyngeal area while the patients are in a supine position during sleep. Participants will be instructed to collect oral fluid at the following time-points in the containers provided (before taking the first dose of study and every 2 weeks after that). The collected oral fluid should be placed in the freezer in a sealed container. This container will be collected after the participant is at the end of their participation. The participant will then wipe the container surface with disinfectant and return to site. If the participant becomes quarantined or hospitalized with COVID-19, a primary contact for the participant will be contacted and if asymptomatic and/or COVID-19 negative the driver will pick up the saliva using the same procedure.

8.5 Hydroxychloroquine Dose Reduction.

In outpatient arms 1 and 3, any AE of \geq Grade 2 or adjusted QTc prolongation to >500ms and attributed as possibly, probably or definitely related solely to HCQ will result in dose holiday and/or dose reduction of HCQ as described in Table 5. No more than 1 dose reductions are allowed.

Table 3: Hydroxychloroquine Dose Reduction Schema

Sub-Study	Dose mg/day	First dose reduction
1	400 mg twice daily	400mg daily
3	600 mg daily	400 mg daily

- If the second dose reduction is not tolerated, then the patient should discontinue the treatment.

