10.0 MEASUREMENT OF EFFECT

10.1 Definitions

Evaluable for toxicity. All participants will be evaluable for toxicity from the time of their first treatment with HCQ or placebo.

Evaluable for primary outcome: Participants who received at least one dose of study drug will be evaluable for the primary outcome as long as they meet the following status for SARS-COV2 PCR: sub-study 1: PCR+ Sub-study 3: PCR negative.

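### In Sub-Study 1 a QTc reading taken after dosing can be labelled pre-treatment, so a drug effect could be misclassified as a baseline finding

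*Protocol*

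**What the plan says.** Protocol section 4.1.1 gives the order of events in Sub-Study 1. At step 6, "IDS randomizes the participant". At step 7 the blinded drug and the telemetry device are delivered. At step 8 a study team member calls and asks the participant to wear the device. The rule there is: "If the baseline, adjusted (Pre-treatment) Qtc is >500 , the patient will be removed from the study". The next sentence offers a reason, "Since the half life of HCQ is many days", and concludes that "the activation of the ZioAT and transmission of the baseline QTc does not need to occur before starting study medication". No maximum interval between first dose and activation is stated.

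Other sections bear on the same reading:

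- **Table 4 (section 9.0)** marks mobile telemetry in the column for assessments before treatment, with no footnote on timing.
- **Section 8.4.1** says of telemetry on treatment: "Dose adjustments will be performed as described below to achieve adjusted QTc <500 ms when necessary".
- **Section 8.5** says that "adjusted QTc prolongation to >500ms and attributed as possibly, probably or definitely related solely to HCQ will result in dose holiday and/or dose reduction".
- **Section 10.1** makes all participants evaluable for toxicity from their first treatment. It also says: "Participants who received at least one dose of study drug will be evaluable for the primary outcome", which for Sub-Study 1 applies if they are PCR-positive.
- **Section 3.2** lists no QTc exclusion for Sub-Study 1.

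The SAP covers Sub-Study 3 only, so it does not settle any of this.

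**The concern.** Step 8 treats the reading as a screen for a condition that the participant brought into the trial, yet allows it to be obtained once the participant is randomised and dosed. Section 7.3 itself states that hydroxychloroquine can prolong the QT interval. A first reading above 500 after dosing may therefore be a drug effect, and the label attached to it decides two things.

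The first is which rule applies: removal from the study, or dose holiday and/or reduction. The second is where the event is counted. A value called baseline is easily taken as pre-existing. The rate of treatment-related adverse events is a secondary objective of Sub-Study 1, and QTc prolongation is the effect that telemetry was added to watch for. The interest is in counting such events correctly, by arm.

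**Working it through.** The plan gives no rate of QTc above 500 and no figure that depends on this rule, so there is nothing of its own to reproduce. The check is mainly a comparison of passages; the arithmetic only shows scale.

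**1. Can the reading be post-dose?** Step 8 allows activation, not just transmission, to follow the first dose. Assuming that the device records nothing before activation, the first trace is then post-dose. The protocol draws the distinction between recording and reading elsewhere: in Sub-Study 3 (section 8.4.2) the baseline ECG is recorded before study drug and only its reading may come later.

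**2. Which rule applies to a first reading above 500 taken after dosing?**

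| Label given | Governing text | Consequence |
|---|---|---|
| Baseline | 4.1.1 step 8 | Removal from the study |
| On-treatment, attributed to HCQ | 8.4.1 and 8.5 | Dose holiday and/or reduction |

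Nothing in the text says which label such a reading takes.

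**3. Where is it counted?** Under section 11.0 an adverse event must develop or worsen during the study. Under section 11.2.5 a condition present at the start is reported as medical history. A post-dose value called baseline can follow the second route. Later telemetry may not correct this: section 8.4.1 says that cardiac assessments after baseline are triggered only by alerts, and the participant has by then been removed.

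**4. Does the half-life argument close the gap?** Section 2.4 reports roughly 2 weeks to steady state in cancer patients. Assume that this equals k half-lives, with k from 3.3 to 5. Then half-life = 14/k, that is 14/3.3 = 4.2 days to 14/5 = 2.8 days. The share of steady-state exposure reached at time t is 1 − 2^(−t/half-life):

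| Delay | Share of steady state |
|---|---|
| 12 hours | 8–12% |
| 1 day | 15–22% |
| 2 days | 28–39% |
| 3 days | 39–52% |
| 7 days | 68–82% |

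The argument supports a delay of hours. It does not support an open-ended one.

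**5. How many readings might be mislabelled?** Expected number = 50 × q × f. Here 50 is the planned size of the HCQ arm, q is the assumed proportion exceeding 500, and f is the assumed fraction of those who do so before a late baseline reading.

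| q | Cases, 50q | f = 0.25 | f = 0.50 |
|---|---|---|---|
| 2% | 1 | 0.25 | 0.5 |
| 5% | 2.5 | 0.6 | 1.25 |
| 10% | 5 | 1.25 | 2.5 |

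Both q and f are assumptions. Telemetry may also be refused (section 8.4.1), so the number at risk is at most 50.

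**6. Would power suffer?** Use a fixed-sample Schoenfeld approximation with hazard ratio 2 and one-sided alpha 0.05: power = Φ(√(d/4) × ln 2 − 1.645) for d events. With all 100 participants having an event, Φ(5 × 0.693 − 1.645) = 0.966. With 95 events, Φ(4.873 × 0.693 − 1.645) = 0.959. This is a ceiling, not the plan's 93%, which allows for incomplete follow-up and interim looks; only the small difference matters. Losing five events is itself more than the table in step 5 suggests.

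**The case against.** The best answer is that the protocol already protects most of what matters.

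- **Analysis sets.** Being removed from the study concerns participation; being evaluable concerns analysis. Section 10.1 keeps dosed participants evaluable for toxicity and, if PCR-positive, for the primary outcome. No passage excludes anyone from analysis because of QTc. This stands: a reader might infer that removed participants drop out of the data, and the text does not say so.
- **Event reporting.** Section 11.0 counts an abnormal diagnostic result as an adverse event if it leads to withdrawal or further tests. Section 11.1.1 collects all serious events after consent, and an adverse event leading to hospitalisation is reported as serious. This largely stands. It still depends on the finding being accepted as new since the start of treatment, which is what the label puts in doubt.
- **Literal reading.** Step 8 limits removal to a pre-treatment value, so a drug-induced one belongs under section 8.5. That is a fair reading, but step 8 then has no qualifying value whenever activation is late, and its two sentences still conflict.
- **Table 4.** A footnote lets oral fluid collected the morning after the first dose serve as the baseline sample, so the before-treatment column is not strictly pre-dose. True, but telemetry has no such footnote, and the nares swab carries an explicit pre-dose requirement.

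A reader might also infer that removed participants are replaced. That appears only in the amendment log and cannot be taken as current text.

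**Conclusion.** The inconsistency is real and present in the current protocol. A post-dose QTc can be called baseline, the same reading can fall under two different rules, and a drug effect could be recorded as pre-existing and so missed in the treatment-related adverse event rate.

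The consequence is limited to misclassification of a few QTc events. Their number cannot be computed from the documents; the illustration gives 0.25 to 2.5 participants, resting wholly on the assumed q and f, on full use of an optional device, and on the assumption that the device records nothing before activation.

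Two stronger conclusions are tempting and not supported. One is that the trial would lose its whole cardiac signal: no event rate is given, and sections 10.1 and 11 retain much of the information. The other is that the arms become unbalanced or power is lost. Removal is decided under blinding and can occur in either arm, so a difference would arise only through a drug effect that the documents do not quantify, and the effect on power is negligible. Nor is this a formal eligibility exclusion, since section 3.2 contains none for QTc. It should be corrected, chiefly for the sake of the safety data.

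**What to change.** Reconcile section 4.1.1 step 8, sections 8.4.1 and 8.5, Table 4 and section 10.1, so that one stated rule covers a first QTc above 500 obtained after dosing. Which clinical rule that is remains the sponsor's decision.

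For the analysis, state that:

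1. The times of first dose and of first QTc reading are recorded for each participant.
2. Only a reading before the first dose counts as baseline; otherwise baseline QTc is missing.
3. Any reading after the first dose is an on-treatment value and, if above 500, is reported in the safety data by arm, whatever action followed.
4. A dosed, PCR-positive participant removed for QTc stays in the toxicity and primary-outcome sets under section 10.1.
5. Time to release for such a participant is handled in a named way, for example by continued follow-up to release or by censoring at removal.

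The cost is protocol wording and two time fields. It needs no additional participants or procedures.

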4.1.2 Sub-Study 3 Outpatient Hospital Workers

1. Healthcare workers will enroll in stations in the ED.
2. Delegated and credentialed clinical investigator sends consent via email/DocuSign and reviews consent form with the participant
3. Conducts e-consent process with the patient and documents via telemedicine/DocuSign
4. If a participant is a member of the PATCH study team, then they are counselled to ensure they do not reveal their own participation during the consenting of participants to Sub-study 1.
5. Eligibility checklist is reviewed and signed by an appropriately delegated and credentialed clinical investigator

The PATCH Trial

6. Participant is randomized by IDS
7. Sub-Investigator orders study drug and PCR test.
8. Nasopharyngeal swab for COVID19, and blood collection if available/possible is performed in the designated area
9. A baseline ECG (6 lead ECG is acceptable) will be obtained if the participant has not had one recently. If the participant has had an ECG in the last 6 months, and they have not started any QT prolonging medications in the interim, the previously obtained ECG can be used.
10. Blinded study drug and 5 oral fluid collection kits are provided to the participant by Study member who reviews dosing of study drug (three pills daily) with the participant.

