Clinical Symptom monitoring: Appropriately delegated and credentialed study team members (as example: CRC) will screen for symptoms 1X per week and if present will document the likely treatment related AEs. Follow up with an appropriately delegated and credentialed physician investigator will be undertaken for assessment and grading of events. Participants will be asked if there have been changes in vision such as distortions of blurred vision. Patients who develop COVID-19 symptoms will be instructed to go to occupational health for nasopharyngeal swab. The rate of conversion to PCR positive in each arm at the 2-month mark will be used to assess the primary endpoint.

Electrocardiogram Recordings: An electrocardiogram (12 lead or 6 lead) will be recorded at baseline prior to the initiation of the study drug. Those participants with an ECG in the last 6 months and no QTc prolonging medications do not need a repeat baseline ECG. One month after starting the study drug a repeat ECG will be performed to confirm excessive QTc prolongation has not occurred. If the QTc has prolonged to >500ms dose reduction as described below will be attempted to achieve a QTc of <500ms. Due to the long half-life of HCQ, study medication can be started before the baseline ECG is read.

Pill diary: Electronic pill diary will be turned in by the participant at the end of the study.

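### Sub-study 3 takes a baseline ECG but states no specific action for a baseline QTc above 500 ms, although sub-study 1 removes such a participant

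*Protocol*

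**What the plan says.** **SS3 baseline ECG.** Protocol 4.1.2 puts eligibility sign-off at step 5, randomization at step 6, the ECG at step 9 and dispensing at step 10. Step 9 accepts an existing tracing on this condition: "If the participant has had an ECG in the last 6 months, and they have not started any QT prolonging medications in the interim". Section 8.4.2 words the condition differently: "Those participants with an ECG in the last 6 months and no QTc prolonging medications do not need a repeat baseline ECG". Footnote 3 of Table 6 lets the baseline ECG be deferred whenever one exists from the last 6 months, with no drug condition. The same footnote describes the ECG as serving research only and lets the later ECGs be deferred as well. On timing, 8.4.2 says that "study medication can be started before the baseline ECG is read".

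**SS3 action on QTc.** Section 8.4.2 attaches a consequence to the one-month repeat ECG: "If the QTc has prolonged to >500ms dose reduction as described below will be attempted". Section 8.5 gives a dose holiday and/or reduction for prolongation attributed to HCQ.

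**SS1 action on QTc.** In 4.1.1 step 8, if the pre-treatment QTc exceeds 500, "the patient will be removed from the study and advised to go to the emergency room". SS1 does not hold the drug for this result, since "transmission of the baseline QTc does not need to occur before starting study medication". Its telemetry is also optional (8.4.1): "Refusal to wear the mobile cardiac telemetry device will not prevent study participation".

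**The concern.** The protocol uses 500 ms as its QTc threshold, and 7.3 acknowledges that HCQ can prolong the QT interval. SS1 says what follows when a participant is already over that threshold at entry. SS3 collects the same kind of information and does not say. Because the SS3 ECG comes after eligibility sign-off and randomization, and may be read after the first dose, it does not control entry, and no stated consequence follows later.

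What is at stake is the safety of individual participants. SS3 enrolls volunteers for prevention over two months. The next scheduled ECG is at one month and can be deferred, so someone who enters above 500 ms has no certain second look.

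**Working it through.** The main check is textual. I looked for any current provision that would require action on an SS3 baseline QTc above 500 ms.

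1. **Exclusions (3.2).** Item 3.2.7 names seven QT-prolonging drugs. Item 3.2.9 opens with "History or evidence of increased cardiovascular risk including any of the following", which may be read as open-ended, but its list has no QTc item. The QTc exclusion in the superseded April protocol applied to sub-study 2 only.
2. **One-month ECG (8.4.2).** The trigger is a QTc that has prolonged to above 500 ms on the repeat tracing. A value already above 500 at entry is not clearly covered. The response is a reduction, which Table 3 sets at 600 to 400 mg daily, not a stop.
3. **Dose reduction (8.5).** This requires attribution to HCQ alone. A pre-treatment value cannot have that attribution.
4. **Dose delay (8.2).** This covers grade 3 and 4 toxicities that are not treatment-related and that HCQ might complicate, with removal from treatment if they do not resolve within 14 days. It needs no attribution to HCQ, so it is the nearest candidate. The fit is only arguable: it speaks of toxicities, it counts a return to baseline as resolution (already met here), and the grade depends on CTCAE tables that the documents do not reproduce.
5. **Ocular toxicity (8.3).** This names retinopathy as the only toxicity that requires HCQ to be discontinued, so it supplies no mandatory stop for QTc.
6. **Off treatment (10.3).** The investigator or treating physician may remove a participant. This applies, but it is discretionary.
7. **SAP.** It uses the ECGs to define the change-in-QTc analysis set and prescribes no action.

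No provision states a specific action.

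**Reuse of an old ECG.** Two cases show how the three wordings differ:
- A QT drug outside the seven, started after the old ECG: 4.1.2 and 8.4.2 require a new ECG; footnote 3 does not.
- A stable QT drug outside the seven, already in use at the old ECG: 4.1.2 and footnote 3 permit reuse; 8.4.2 does not.

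**Size.** The documents give no prevalence of a baseline QTc above 500 ms, so no count can be derived. To show only how far the answer depends on that input, assume a prevalence p of 0.1% to 1%, N of 200 to 250 (target and screening numbers in 8.4.2), and half on HCQ:
- Expected HCQ recipients affected = N × p / 2: from 200 × 0.001 / 2 = 0.1 to 250 × 0.01 / 2 = 1.25.
- Chance of at least one = 1 − (1 − p/2)^N: from 1 − 0.9995^200 = 0.095 to 1 − 0.995^250 = 0.714.

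The spread comes almost entirely from the assumed p. The upper end also counts all 250 screened, including baseline PCR-positive participants who may leave. The cardiovascular exclusions may push the true figure toward the low end.

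**The case against.** The two sub-studies differ. SS1 enrolls symptomatic, PCR-positive people aged 40 or over on 800 mg daily, and SS3 enrolls working staff on 600 mg daily, so identical rules are not self-evidently needed. That stands as a reason why the SS3 action might differ; it does not explain having none for an ECG that the plan collects.

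A reader might infer that SS1 is protected before dosing and SS3 is not. The documents do not support that: SS1 also allows drug before the baseline QTc arrives and allows telemetry to be refused. The difference is confined to what happens once a high value is known.

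A reader might also infer that nothing but discretion applies in SS3. That goes too far, because 8.2 can be argued to reach such a case.

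The reuse wordings could be presented as a serious three-way conflict. They are close to a drafting variation. Two of the three carry a drug check, 3.2.7 already excludes seven drugs, and 7.3 requires SS3 participants to consult the investigator before taking anything except Tylenol and advises against combining HCQ with arrhythmogenic drugs. In the extracted table it is also unclear which row footnote 3 belongs to. What remains is a few participants for whom footnote 3 alone would waive a new ECG.

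Finally, it might be said that a stop rule would cost primary-outcome data. The continued-procedures paragraph in 10.3 does concern withdrawal by patient choice, but the SAP's amendment table records more generally that participants who discontinue study medication can complete study procedures.

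**Conclusion.** The point holds as a safety gap of limited reach. SS3 obtains a baseline ECG and states no specific action for a QTc above 500 ms, while SS1 removes such a participant. Following the stated SS3 rules could leave an uninfected volunteer with that value on study drug for a month or longer, unless a physician uses discretion or reads 8.2 broadly. The inconsistent reuse wording is a minor accompanying matter.

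Few people are affected, and how few cannot be derived from the documents; the illustrative range above is not an estimate. It would be tempting to add that the trial's results are compromised. The documents do not support that. An old tracing that predates a QT drug may add noise to the change-in-QTc outcome, but with randomization and placebo control it is not expected to favor an arm. Power and alpha are untouched. The change is still worth making because it is specific, cheap and protects participants.

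**What to change.** In protocol 4.1.2 step 9 and 8.4.2, require the SS3 baseline ECG, new or reused, to be read before or promptly after the first dose. If QTc is above 500 ms, stop study drug, refer the participant for evaluation, and continue the 4-week and 8-week swabs and the weekly calls.

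The follow-up clause agrees with the SAP's amendment table and is worth stating in the rule itself: one dose makes a baseline PCR-negative participant evaluable under 10.1, and the SAP does not impute missing values. Because the rule acts on a pre-treatment value read blind to arm and keeps follow-up, it is not expected to bias the comparison.

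As a minor edit, add to Table 6 footnote 3 the 4.1.2 condition that no QT-prolonging drug has been started since the old ECG, and word 8.4.2 to match.

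The cost is wording in three places, prompt reading of each baseline ECG, and a rare early stop of study drug.
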